## Abstract

**Background:** Severe grief reactions (SGR), or complicated grief, are experienced by 2-3% of the population after the loss of a loved one, and can be associated with declining health, social distress, increased use of healthcare resources and higher mortality. SGR can be related to the circumstances of the patient at the end of life, particularly in deaths that were unexpected or traumatic, when the family member was unprepared or unsupported. The COVID-19 pandemic has affected many aspects of end-of-life care. For example, infection control measures may reduce interactions between long-term care residents and family members, and have often limited in-person family visiting to the final hours of life, or no visiting at all for patients with COVID-19. Anecdotally, this disruption of normal interactions has been difficult for patients and families alike, and we know that isolation and lack of closure with a loved one can contribute to the risk of SGR. The prevalence of SGR is expected to rise amid increased challenges in supporting a surge of people with SGR due to physical distancing and limited bereavement resources.

**Methods:** The proposed mixed methods explanatory study includes both retrospective and prospective data collection. The quantitative components will principally consist of natural experiments to identify patient/FM characteristics indicating a high risk of SGR during the COVID-19 pandemic. The qualitative components will deepen our understanding of the impact of COVID-19 on bereavement, while providing formative evaluation for the virtual support groups. Study subjects will include all patients who died in an acute care facility in Ottawa (The Ottawa Hospital, Queensway-Carleton Hospital, and Hôpital Montfort) from November 11, 2019 until August 31, 2020, and their primary contact (as indicated in their medical record).

**Significance:** Early identification of FMs at risk of SGR provides an opportunity for early intervention with the hope of preventing or reducing the severity of the SGR, but it also enables prioritization of those in greatest need, should demand exceed resources. Moreover, because we are still early in the pandemic, we are able to collect clinical data about the circumstances of the death, and consistently collect bereavement data for family members of people who died before and after the pandemic struck, and before and after the availability of virtual support groups. We therefore have a unique opportunity to conduct two natural experiments- studying the impact of the COVID pandemic on bereavement, and studying the effect of virtual support groups on symptoms.

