## RESEARCH OBJECTIVES

1. Determine the impact of the COVID-19 pandemic on the bereavement experience of FMs.
2. Identify patient/FM characteristics indicating a high risk of SGR during the COVID-19 pandemic.
3. Assess the feasibility, acceptability and preliminary efficacy of virtual support groups (VSG).

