## METHODS

### Design

We propose a mixed methods explanatory design, including both retrospective and prospective data collection. The quantitative components will principally consist of natural experiments to address objectives #1, #2, and #3. The qualitative components will deepen our understanding of the impact of COVID-19 on bereavement (Objective #1), while providing formative evaluation for the VSG (Objective #3).

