## **Phase 3: Virtual Support Groups**

FMs who participate in the prospective bereavement data collection (i.e. Phase 2) will be invited to attend a virtual support group (VSG) led by Bereaved Families of Ontario- Ottawa (BFO). In pre-COVID times, BFO presented monthly “*Support and Share*” nights with guest speakers, followed by breakout peer support groups for all different types of losses: loss of child, spouse, parent, loss by suicide, etc. These groups are facilitated by trained volunteers with a shared loss and include between 75 and 150 participants. These Support and Share Nights serve as intake sessions- interested participants from the breakout groups can attend “*Closed Groups*” where a smaller group of participants (up to 12) explore their grief more deeply. These run over 8-10 consecutive weeks with the same group of participants. They are led by trained facilitators who have experienced similar losses. Each week has a different theme, based on evidence-based components of bereavement support (e.g. writing a letter to the deceased). The sessions were put on hold in March by the pandemic, but

BFO plans to begin holding these *Closed Groups* by videoconference (these will be the VSGs) again in September 2020.

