All participants in the prospective bereavement data collection component of this study will be invited to participate in the VSGs (see approved Virtual Support Group Information Sheet), regardless of the severity of their symptoms. Those with severe symptoms (indicated by an ICG-r score  $>25$ ) will be notified that their symptoms are considered to be severe, with a suggestion to attend the VSGs. A recent meta-analysis of psychological interventions for grief found higher effect sizes in studies of participants who were  $>6$  months post-loss, and those with higher baseline symptom levels. However, no participant in our study will be randomized to any treatment assignment, and the decision to attend the VSG will be left to the FM. Family members will participate in the virtual support group as part of routine care available to them by BFO. The support group is not a study-specific intervention, nor will any research team members be involved in the administration of the virtual support group, and no data will be collected from the virtual support group online sessions. The scope of the research study related to the virtual support group is to a) inform the 200 bereaved family participants about the support group, so that they may seek out this care available to them and b) conduct qualitative interviews with 20 participants who attended the virtual support group (see Phase 4 below). As such, while we will obtain consent for conducting the Phase 2 questionnaires and the Phase 4 qualitative interviews, consent will not be obtained for participation in the virtual support groups. Any participant who expresses suicidal ideation or intention, or other concerning features of severe grief reaction, will be referred for urgent assessment and professional support through their family physician or the emergency department, as per usual practice with BFO.

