### Phase 1-3: Quantitative Data Analysis

To address research objectives #1 and #2, we will divide the patients (and FMs) into three groups:

- a. Pre-COVID: Deaths that occurred in an acute care hospital before the impact of the pandemic was first felt in Ottawa (November 1st, 2019–February 29th, 2020): approximately 160 patients.
- b. COVID: Deaths that occurred in an acute care hospital due to COVID-19 (March 1st – August 31st, 2020). Approximately 250 COVID-19 deaths have been reported between January and June 2019 in Ottawa by Ottawa Public Health, of which preliminary data suggest approximately 80 patients died in acute care.
- c. Non-COVID: Deaths that occurred in an acute care hospital between March 1st – August 31st, 2020 but were not COVID-19 related: approximately 160 patients.

To assess the overall impact of the pandemic, we will perform statistical comparisons of clinical and end-of-life care metrics for the Pre-COVID vs. COVID and Non-COVID groups combined. Patients will be matched based on their health and demographic profiles in a 2:1:2 ratio (2 decedents in pre-COVID period: 1 decedent during the pandemic who died of COVID-19: 2 decedents who died during the pandemic of non-COVID-19 causes). We will compare the COVID vs. Non-COVID groups to determine how much of the impact was specifically associated with COVID infection as opposed to the pandemic in general. Pairwise comparisons will be performed using an unpaired t-test or Mann-Whitney test as appropriate for the distribution of the data. We will then also use logistic regression analysis to identify factors associated with an ICG score  $>25$  (i.e. severe scores).

To address research objective #3, we will compare the changes in ICG scores between baseline and 6-months post-baseline for FMs who did versus did not participate in the VSGs (i.e. the difference in differences). This comparison is important since grief symptoms typically improve over time even without intervention. In addition, group allocation is not random and so our analysis may be

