## TIMELINE

Month	2020				2021										
	S	O	N	D	J	F	M	A	M	J	J	A	S	O	
Ethics Approval (September-November 2020)															
Phase I: Retrospective chart review (Quantitative- October 2020 – February 2021)															
Phase II: Prospective Bereavement Data Collection (Quantitative- October-December 2020, April-June 2021)															
Phase III: Virtual Support Groups (October 2020 – March 2021)															
Quantitative Data Analysis (June – August 2021)															
Phase IV: FM Interviews (November 2020 – June 2021)															
Qualitative Data Analysis (January - August 2021)															
Knowledge Translation and Dissemination (August -October 2021)															

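### No family member is assessed before the pandemic and no cohort precedes the virtual support groups, so the family-member contrasts answer narrower questions than the natural experiments described

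*Combined protocol and SAP*

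**What the plan says.** The Abstract (Significance) promises consistent bereavement data for family members of people who died "before and after the pandemic struck, and before and after the availability of virtual support groups", and concludes that two natural experiments are possible. Research Objectives gives Objective 1 as "Determine the impact of the COVID-19 pandemic on the bereavement experience of FMs". The Design section adds: "The quantitative components will principally consist of natural experiments to address objectives #1, #2, and #3".

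Phase 1-3: Quantitative Data Analysis defines the Pre-COVID group as "Deaths that occurred in an acute care hospital before the impact of the pandemic was first felt in Ottawa", dated 1 November 2019 to 29 February 2020, with about 160 patients. The pandemic-period groups cover 1 March to 31 August 2020: about 80 COVID-19 deaths, and a Non-COVID group described as "2020 but were not COVID-19 related: approximately 160 patients". Patients and family members are split in the same way.

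Phase 2 approaches family members no sooner than six months after the death. The Timeline reads "Phase II: Prospective Bereavement Data Collection (Quantitative- October-December 2020, April-June 2021". On the support groups, Phase 3 says the closed groups will run "by videoconference (these will be the VSGs) again in September 2020", while the Timeline shows them from October 2020 to March 2021. Phase 3 also states: "All participants in the prospective bereavement data collection component of this study will be invited to participate in the VSGs".

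**The concern.** A before/after natural experiment needs some people observed under the earlier condition. For grief during the pandemic, that would be family members whose bereavement ran its course, or was at least measured, before the pandemic. For support-group availability, it would be a cohort bereaved or assessed before the groups opened. The calendar appears to provide neither.

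This matters because the protocol names pandemic mechanisms that act after the death. The Abstract cites physical distancing and limited bereavement resources. Background and Rationale cites distancing rules that may reinforce avoidance and rule out in-person treatment. If all three groups grieve under these conditions, their effect largely cancels in the comparison. A small or null ICG-r difference could then be taken to mean that the pandemic had little effect on bereavement, when the shared part of the effect was never contrasted. The protocol carries no caution on this; its confounding caveat concerns support-group attendance only.

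For Objective 3, the Significance paragraph describes a stronger design than the one analysed, and readers may give the result more causal weight than it can bear.

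**Working it through.** The plan states no figure for this point, so the check is date arithmetic.

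**Inputs.** Pre-COVID deaths 1 November 2019 to 29 February 2020 (121 days), and pandemic period from 1 March 2020 (Phase 1-3: Quantitative Data Analysis). Six-month minimum (Phase 2). Baseline October to December 2020 and follow-up April to June 2021 (Timeline). Last eligible death 31 August 2020 (Study Setting). Support groups from September 2020 (Phase 3) or October 2020 (Timeline). Assumption: Pre-COVID deaths spread evenly over the 121 days.

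**Step 1: is any ICG-r taken before the pandemic?** The earliest possible assessment under the six-month rule alone is 1 November 2019 + 6 months = 1 May 2020, which is 61 days after 1 March 2020. On the Timeline, baselines open on 1 October 2020, 214 days into the pandemic period. No ICG-r is pre-pandemic.

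**Step 2: how much Pre-COVID bereavement falls in the pandemic?** Share = (assessment date − 1 March 2020) / (assessment date − date of death).

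| Assessment date | Days since 1 March 2020 | Death 1 Nov 2019 | Death 29 Feb 2020 | Mean over 121 days |
|---|---|---|---|---|
| 1 October 2020 | 214 | 214/335 = 64% | 214/215 = 99.5% | 79% |
| 15 November 2020 | 259 | 259/380 = 68% | 259/260 = 99.6% | 82% |
| 15 May 2021 | 440 | 440/561 = 78% | 440/441 = 99.8% | 88% |

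The Abstract (Methods) gives 11 November 2019 as the start of the death window. With that date, the lowest share at 15 November 2020 becomes 259/370 = 70%, so the conclusion does not depend on which start is correct. For deaths from 1 March 2020 onward the share is 100%.

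**Step 3: is there a cohort before support-group availability?** By date of death: the last eligible death is 31 August 2020, before either start date, so every death is before availability and none is after. By date of assessment: with a September start, baselines open 30 days after 1 September and none precedes availability. With an October start, baselines and groups begin in the same month, so a few October baselines might precede the first session. Those family members are still invited and are followed up after the groups have begun, so they do not form a separate cohort without access.

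**Step 4: what contrasts do exist?** Pre-COVID deaths (about 160) were not exposed to pandemic conditions at the death itself, such as the visitor restrictions described in Background and Rationale. For the support groups, about 100 of 200 family members are expected to attend (Study Participants), leaving 200 − 100 = about 100 concurrent non-attenders, each with a baseline and a six-month ICG-r.

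**The case against.** The strongest reply is that the pandemic split in the Significance paragraph is by date of death, and on that basis it is accurate. Many of the mechanisms the protocol names act at or around the death: visiting limits, infection control, lack of closure, guilt about transmission. The analysis section ties the overall impact of the pandemic to clinical and end-of-life care metrics, which are fixed at death, and spells out no Pre-COVID versus pandemic test of ICG-r. Objective 1 also has a qualitative arm. All of this stands, and it is why the contrast is narrower rather than void. It does not remove the point: Objective 1 is worded in terms of family members' bereavement experience, family members are put into the same three groups for that objective, and some of the named mechanisms act after the death.

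On Objective 3, the plan already says that nobody is randomised, that attenders may have more severe symptoms, and that covariates will be added where baseline differences exist. It claims only preliminary efficacy. That also stands. What remains is the before/after-availability claim, which the dates cannot deliver.

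A reader might infer that neither comparison has an unexposed group and that the study cannot show any of its intended effects. The documents do not support that. Pre-COVID deaths are unexposed at the death, and non-attenders are a concurrent control.

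A reader might also turn the 82% share into a dilution factor for the ICG-r difference. That would require the pandemic's effect on grief to be proportional to calendar time, for which the documents give no basis. Nor would a gradient in ICG-r by months from death to 1 March 2020 rescue the question: at a given assessment date that interval differs from time since death only by a constant, and the protocol itself says grief usually eases with time.

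**Conclusion.** The point holds in a limited form. No family member is assessed before the pandemic. No family-member cohort precedes support-group availability by date of death or, apart from possibly a few October 2020 baselines if the October start applies, by date of assessment.

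The Pre-COVID versus pandemic family-member contrast estimates the effect of a death during versus shortly before the pandemic, among people who all grieved mostly during it. It largely misses effects acting after the death. It remains valid for circumstances of death, and the chart-based comparisons are untouched. The support-group analysis is a concurrent, covariate-adjusted observational comparison.

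The absence of any pre-pandemic ICG-r follows from the six-month rule alone. The 82% average also assumes evenly spread deaths, a 15 November 2020 assessment and the protocol's own 1 March 2020 boundary; across the three assessment dates tabulated the mean is 79% to 88%. No numerical bias in ICG-r can be derived from these figures. The change is worth making because it alters what the study may conclude.

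**What to change.** 1. In the Abstract (Significance), Research Objectives and Design, restate the family-member part of Objective 1 as the effect of a death during versus shortly before the pandemic, among family members who were all assessed during it.
2. Reserve the overall impact of the pandemic for the chart-based clinical and end-of-life metrics, as the analysis section already does.
3. Add a sentence that a null ICG-r contrast between the Pre-COVID and pandemic groups does not imply that the pandemic had no effect on grief, because all groups were bereaved largely under pandemic conditions.
4. In the Abstract (Significance), delete the clause on support-group availability. There and in Design, describe Objective 3 as an adjusted observational comparison of attenders and non-attenders rather than a natural experiment.
5. Reconcile the support-group start in Phase 3 (September 2020) with the Timeline (October 2020), and state whether any baseline may precede the first session.

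The cost is wording only, with no new data, visits or sample. The price is a narrower claim for the family-member results.

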## BACKGROUND AND RATIONALE

When people die, it is normal for their bereaved family members (FMs) to experience grief. This grief usually diminishes, but in some cases FMs suffer from severe grief reaction (SGR) with intense yearning or separation distress, as well as emotional, cognitive and functional impairment lasting months or years. SGRs have been variously labelled as Complicated Grief (CG), Prolonged Grief Disorder (PGD), or Persistent Complex Bereavement-Related Disorder (PCBRD, included in the Diagnostic Services Manual ver. 5), and may also feature other psychiatric morbidity such as depression or post-traumatic stress disorder (PTSD). SGRs are linked with declining health, use of healthcare resources, and even death.

The COVID-19 pandemic has affected many aspects of end-of-life care, even for those who die of illnesses other than COVID-19. For those admitted to acute or long-term care, visitor restrictions have significantly impacted family presence in the final hours of life. Videoconferencing and telephone interactions are not feasible for many elderly or dying patients, and are not recommended when patients are actively dying. Supportive interactions from healthcare providers are also limited by infection control measures. COVID-19 can also enhance feelings of guilt; FMs may have unwittingly transmitted COVID-19 during a visit, or the FMs may feel guilt for not having taken them out of a Long-Term Care facility prior to an outbreak. All of these factors will likely increase the risk of SGR. Moreover, despite the increase in mortality rate caused by a pandemic, the disruption in normal services (e.g. cancer care) actually results in reduced use of hospice and palliative care, which are known to protect against SGR.

Many bereaved FMs would appreciate bereavement support, and bereavement support has been identified as a clinical and research priority. Yet few acute or long-term care settings (where most death occurs in Canada) have devoted resources toward bereavement screening or support, so many FMs seek support from therapists or community-based bereavement groups outside of the public healthcare system.

There are effective treatments for established SGRs (i.e. >6 months post-death), including individual psychotherapy tailored to Complicated Grief. Group therapy may also be beneficial, as illustrated in a naturalistic controlled trial of bereavement counselling delivered through a community-based organization. But these therapies may not be as effective during the pandemic; Glickman et al. found that feelings of guilt and avoidance were two of the most important mediating factors mediating the response to complicated grief treatment. Since feelings of guilt appear to be common in COVID-19 deaths, and social distancing rules have the potential to reinforce avoidant behaviour, these could undermine the effectiveness of standard therapies. More importantly, SGR treatments are usually based on in-person sessions; these are limited resources that may not be able to accommodate a major surge in SGR incidence triggered by the pandemic, and physical distancing rules would preclude their use in a pandemic.

Internet-based interventions have shown promise in preventing mental disorders and treating symptoms of post-traumatic stress. A randomized controlled trial of an email-based intervention was shown to improve complicated grief symptoms, with a high acceptance and low drop-out rate. Internet-based self-help interventions have also improved grief symptoms in bereaved older adults. However, there is little data on the use of virtual group sessions as part of a bereavement support program- this is a critical gap in the literature, given that group therapy is one of the more accessible and scalable options available. Many community-based organizations are planning to provide their

usual support group sessions virtually, including Bereaved Families of Ontario, which has been supporting bereaved FMs for more than 40 years.

## RESEARCH OBJECTIVES

1. Determine the impact of the COVID-19 pandemic on the bereavement experience of FMs.
2. Identify patient/FM characteristics indicating a high risk of SGR during the COVID-19 pandemic.
3. Assess the feasibility, acceptability and preliminary efficacy of virtual support groups (VSG).

## METHODS

### Design

We propose a mixed methods explanatory design, including both retrospective and prospective data collection. The quantitative components will principally consist of natural experiments to address objectives #1, #2, and #3. The qualitative components will deepen our understanding of the impact of COVID-19 on bereavement (Objective #1), while providing formative evaluation for the VSG (Objective #3).

